#### **Part A:**

#### **Primary Objective**

- To evaluate parenteral nutrition prescriptions in hospitalized patients
- **Secondary Objectives**
- Describe patient population according to the pathology that caused the hospitalization
- Record the indication that determined the need for PN and whether they are medical, surgical or ICU patients
- Assess updated Charlson co-morbidity index (CCI)
- Record the number of days with intakes less than 50% of requirements or NPO before PN was prescribed
- Perform a nutritional assessment which includes: weight at admission (if recorded in chart) and at time of starting PN, height, body mass index (BMI), Subjective Global Assessment (SGA), albumin and estimate of nutritional requirements.
- Record the initial PN prescription in terms of energy and proteins
- Record how many days it took to reach the nutritional requirements estimated by the dietitian
- Compare energy received as a goal with calculated energy requirements using published equations
- Record the number of times PN was interrupted
- Record the total number of PN days the patient received
- Determine the type of line (central or peripheral) and number of days with peripheral and/or central lines.

- Determine the type of vascular access (if central line)
- Record laboratory results once a week to assess potential metabolic complications associated with PN
- Record catheter related infections, whether suspected or confirmed
- Record any other complications deemed related to PN
- Record number of antibiotic-days to treat catheter-associated infections
- Record the reason why PN was discontinued
- Record total length of stay
- Record in-hospital mortality and cause of mortality during PN as well as during entire hospital stay

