### **Study design**

This is a prospective study that will evaluate the indications of parenteral nutrition in an inpatient setting. As part of their PN prescription, patients will receive either standard lipid (Intralipid) or OO-based lipid emulsion (ClinOleic), alternately depending on their time point of PN start, i.e. one person will receive Intralipid, the next one ClinOleic, etc. We will collect information from patients that have started with parenteral nutrition during their hospitalization and that are hospitalized in medical, surgical or ICU wards. We will also collect retrospective data of 100 patients to compare if the actions of the nutrition team and results change with respect to the prospective data.

Inclusion Criteria:

- Patients 18 years or older

- Patients that are expected to require PN for 5 days or more during their hospitalization
- Patients hospitalized in medical, surgical or ICU wards
- Signed informed consent either from the patient, their legally authorized representative or a direct family member

Exclusion Criteria:

- Patients without PN during their hospitalization

**Part A:** Patients will be approached when they start with PN during their hospitalization and will be followed until their last day of PN or, if occurred before PN ends, death. **Part**

**B:** For the proposed study, we will start PN as usual, according to the patients needs. We will randomly assign patients to receive either Intralipid or ClinOleic as the lipid emulsion in the PN. The amount of calories from the lipid emulsion will be equivalent.

Patients will be followed for one week after their last day on PN and, in addition, major outcomes such as mortality and length of stay will be assessed during the entire hospitalization.

Information regarding the patients nutrition will be obtained from the hospital chart and by direct communication with the PN team (dietitian, nurse, pharmacist) after signed informed consent.

We will analyze the nutritional indications and laboratory results of patients hospitalized in different units who are starting with PN alone or in combination with enteral or oral feeding twice a week. We will use a registry to enter the data.

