## **Statistical analysis**

**Part A:** Descriptive statistics will be performed. Results will be expressed as absolute numbers and percentages, mean  $\pm$  standard deviation (SD) or median (minimum; maximum) depending on the variable types and distributions, separately for the prospective and the retrospective dataset.

For the prospective study, multivariate logistic regression will be performed to identify risk factors associated with specific PN prescription: for example, inadequate administration of PN. In addition, data from the prospective study and the retrospective chart review will be compared by unpaired t-test, Mann-Whitney-test or chi-square test as appropriate. A p value  $<0.05$  will be considered statistically significant. **Part**

**B:** For the Intralipid and the ClinOleic analysis, all variables will be tested for normal distribution (Shapiro Wilks test). *Primary outcome* is length of stay (in days). The Intralipid and ClinOleic groups will initially be compared with unpaired t-test or Mann-Whitney test as appropriate. *Secondary outcomes*: other clinical outcomes (days in ICU, antibiotic-days, infections, mortality) will also be analyzed the same way initially. For secondary outcomes that may change over time, i.e. hs-CRP, pre-albumin and other laboratory results, BMI, arm circumference, hand grip strength, changes will be compared between groups using unpaired t-test or Mann-Whitney test as appropriate. To account for possible covariate effects (eg. age, baseline BMI, Charlson comorbidity index), regression methods such as generalized linear models will be employed. All tests will be based on two-sided alternatives and a test will be considered statistically significant using alpha=0.05. SAS Enterprise Guide 4.1 software (SAS Institute Inc., Cary, NC, USA) will be used.

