## **Feasibility and Sample Size**

**Part A:** Based on previous studies, there are about 200 in-patients per year receiving PN. All patients will be assessed as per standard medical guidelines for PN and it is expected that 90% will agree to participate in the project. We calculate that we will have enrolled about 50 patients for Part A, before we start with part B. We will later include 150 more patients from Part B to have a total of 200 patients. We will compare the data obtained with 100 retrospective patients to see if the actions of the nutrition team changed since we started the project.

**Part B:** When we receive the ClinOleic in the hospital, patients will receive either SO-based lipid emulsion (Intralipid= 150 patients) or OO-based lipid emulsion (ClinOleic=150 patients) on an alternate basis (one-to-one) for the duration of the PN.

The total number of patients including part A and part B is estimated to be 350 patients. It is expected to take about one and a half years to recruit this number of patients.

For the Intralipid and ClinOleic analysis, we based our sample size on a study that evaluated the use of either SO or SO + fish oil (FO) in 206 patients with gastrointestinal or colonic cancer during 7 days after surgery and found that the patients that were given the FO treatment had significantly shorter length of stay than the SO group (Mean (SD) 15(5) versus 17(8) p= 0.041). Also, they had fewer infectious complications (50). Another study compared soybean oil and soybean oil+FO in 57 elderly patients with colorectal cancer. In the treatment group, there were fewer infectious complications and incidences of systemic inflammatory response syndrome (SIRS), and shorter lengths of hospital stay were observed(51).

Based on this, we estimate that a sample size of 150 in each group with a power of 0.8 and alpha of 0.05 will be sufficient to show a similar difference in length of stay between the two groups (soybean or ClinOleic) using the online sample size calculation provided by G.W. Snedecor & W.G. Cochran  
<http://www.biomath.info/power/ttest.htm>.

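### The Part A comparison of prospective and retrospective patients uses different data sources, so for recording-dependent items a difference between periods can reflect recording rather than changed care

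*Combined protocol and SAP*

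**What the plan says.** Prospective patients: the Study design section states "Information regarding the patients nutrition will be obtained from the hospital chart and by direct communication with the PN team (dietitian, nurse, pharmacist", once consent is signed. The consent condition ties this sentence to the prospective cohort.

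Comparison patients: the same section plans to collect "retrospective data of 100 patients to compare if the actions of the nutrition team and results change" relative to the prospective data. The Feasibility and Sample Size section, Part A, repeats the purpose: "We will compare the data obtained with 100 retrospective patients to see if the actions of the nutrition team changed since we started the project". The source is named only in the Statistical analysis section, Part A, where "data from the prospective study and the retrospective chart review will be compared by unpaired t-test, Mann-Whitney-test or chi-square test as appropriate", with p below 0.05 counted as significant.

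Size of the prospective set: about 50 patients are enrolled before Part B starts, and then "We will later include 150 more patients from Part B to have a total of 200 patients".

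The Part A secondary objectives include two items that depend on recording or judgement: "Record catheter related infections, whether suspected or confirmed" and "Record any other complications deemed related to PN". They also include the number of PN interruptions and the days taken to reach estimated requirements. The Measurements paragraph adds reasons for interruption and total intake, including enteral and oral.

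Follow-up: Study design follows Part A patients to the last PN day or death, and Part B patients for one further week. It states no window for the retrospective set.

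**The concern.** The comparison is meant to show whether the nutrition team's actions, and results, changed. If one period is measured from the chart plus a live informant and the other from the chart alone, the measuring instrument changes at the same moment as the care being judged. An interruption, its reason or a patient's oral intake can be supplied or clarified by the dietitian, nurse or pharmacist in the prospective period. In a chart review, what was not written down is lost.

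This is a measurement difference, so adjusting for case mix or selecting the 100 charts more carefully would not remove it. It can produce an apparent change where there was none, and it can also hide a real one. Suppose charts capture 70% of events and prospective capture is complete. A true fall from 20% to 14% would then be observed as 0.70 × 20% = 14% against 14%, which is no change at all.

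The extra informant is also the team whose actions are under assessment, and it informs on one side only.

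**Working it through.** The documents give no power, effect size or expected rate for this comparison, so there is no stated figure to reproduce. The check has two parts.

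**1. The two data sets side by side**

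| Feature | Prospective | Retrospective |
|---|---|---|
| Source of nutrition information | Chart plus direct contact with the PN team | Chart review |
| Patients | 50 + 150 = 200 | 100 |
| Common form or definitions | None stated | None stated |
| Follow-up | Last PN day or death (Part A); one week longer (Part B) | None stated |

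I found no sentence that limits the comparison to items available from charts in both periods.

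**2. How large the effect could be**

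Inputs from the documents: n₁ = 200, n₂ = 100, alpha 0.05. The two-sided statement stands only in the Part B paragraph, so two-sided is assumed here. The bloodstream-infection range of 1.3% to 39% in the Introduction is used only to bound the event rate p.

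Inputs assumed: the true rate p is the same in both periods, prospective capture is 100%, and chart capture c is 50% to 90%.

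The expected observed rates are a = p and b = p × c. The test is the pooled two-proportion test, equivalent to the uncorrected chi-square:

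- pooled rate m = (200a + 100b)/300
- null standard error s₀ = √[m(1 − m)(1/200 + 1/100)]
- actual standard error s₁ = √[a(1 − a)/200 + b(1 − b)/100]
- false-significance rate = Φ[(a − b − 1.96 s₀)/s₁] + Φ[(−(a − b) − 1.96 s₀)/s₁]

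Worked case, p = 20% and c = 70%:

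- a = 0.20, b = 0.14, m = (40 + 14)/300 = 0.18
- s₀ = √(0.18 × 0.82 × 0.015) = 0.0471, so 1.96 s₀ = 0.0922
- s₁ = √(0.0008 + 0.001204) = 0.0448
- Φ[(0.06 − 0.0922)/0.0448] = Φ(−0.72) = 0.236, and the other tail is below 0.001

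The test is therefore significant in about 24% of studies with no true change.

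| True rate | c = 90% | c = 80% | c = 70% | c = 50% |
|---|---|---|---|---|
| 1.3% | about 5% | about 5% | about 5% | about 6% |
| 10% | 6% | 8% | 12% | 30% |
| 20% | 7% | 13% | 24% | 60% |
| 39% | 10% | 26% | 52% | 94% |

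With equal capture the rate is 5% throughout. The normal approximation is poor in the 1.3% row. The apparent rate ratio is 1/c whatever the true rate: 1.11, 1.25, 1.43 and 2.0 across the columns.

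The table applies to yes/no items. Number of interruptions and days to reach requirements would be compared by other tests, and it does not give a figure for them.

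**The case against.** The strongest reply is that the asymmetry is narrow and its effect is unmeasured. Much of this stands.

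- The sentence on team contact covers information about nutrition. It does not say that infections or complications are learned from the team, and those items are listed without a source. They belong here only by extension, because suspected cases and attribution to PN depend on what someone records.
- The twice-weekly review concerns nutritional indications and laboratory results. It mentions neither team contact nor complications, so it is not evidence of closer complication surveillance.
- Low intake before PN precedes enrolment and is looked up after the fact in both sets, so it is a weak example.
- That the comparison set uses charts only is inferred from its description. No sentence excludes other sources.
- Initial prescriptions, PN and line dates, laboratory values, length of stay and mortality are ordinary chart data.
- The comparison is not among the listed Part A objectives.

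A reader might infer that prospective complication rates will look higher. The documents do not support that. They give no capture rates, and an informant reporting on its own work could under-report as easily as add events. Nor can the larger entries in the table be read as the expected error rate, because they combine common events with poor chart capture, both assumed.

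The reply does not remove the core. Nutrition-process items are what a comparison of team actions rests on, the sources for them differ as written, and the plan has no safeguard.

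**Conclusion.** The point holds in a limited form. For items that depend on completeness of recording, the planned tests cannot separate changed care from changed recording.

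The direction is unknown, and the size rests on assumed capture. With complete prospective capture and 70% chart capture, false significance is about 12% at a 10% event rate and 24% at 20%. At 90% capture it is about 6% and 7%, rising to 10% at a 39% rate. For rare events it stays near 5%.

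Unequal follow-up may add to the problem for infections and complications. The 150 patients drawn from Part B are observed for a week after PN, and no window is stated for the retrospective set. If the Part B follow-up is used, chart-only abstraction would not by itself make those counts comparable.

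The Part B lipid comparison, including its primary outcome, is not affected, because both groups are followed prospectively in the same way. This is worth correcting, but it bears on a secondary comparison.

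**What to change.** 1. Add a source flag to the registry for each item (hospital chart, or contact with the PN team). It has to be set during collection, because the sources are hard to separate afterwards.
2. State in the Statistical analysis section, Part A, that the between-period comparison uses only items abstracted from the hospital chart in both sets, with the same form, definitions and follow-up window. For infections and complications the window could, for example, end at the last PN day in both sets.
3. For infections, compare only chart-confirmed cases. The documents do not define confirmed, so one definition must be written and applied to both sets.
4. Report items learned from the PN team descriptively, for the prospective cohort only.

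The cost is one registry field, a few sentences in the analysis section and a written infection definition. The downside is that fewer items are compared between periods, and suspected infections and judged complications drop out of the comparison.

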Intralipid is a soybean oil (SO) intravenous fat emulsion, available since 1961, rich in omega-6 polyunsaturated fatty acids (PUFA) and may enhance the generation of arachidonic acid-derived eicosanoids that could exaggerate the inflammatory response during stress and trauma (26). This pro-inflammatory effect may be detrimental. For example, in a prospective, randomized, controlled study comparing the vascular, metabolic, immune and inflammatory effects of 24h- infusion of parenteral nutrition (PN) with SO-based lipid emulsion (Intralipid), olive oil-based lipid emulsion (ClinOleic), lipid free and normal saline in 12 healthy subjects, the authors found that Intralipid increased blood pressure and altered endothelial function (27). A recent ASPEN position paper (28) reviewed the literature on lipid emulsions. While the current available, standard SO-based lipid emulsion like Intralipids meet the needs of most PN patients, alternative oil-based fat emulsions, like olive oil (OO) are used extensively in Europe and have been shown to be less proinflammatory and immunosuppressive due to different metabolic pathways. Patients receiving these alternative lipid emulsions may have better clinical outcomes but further research is needed to identify which type of lipid emulsion or which combination of oils may be most clinically useful for specific patient populations. SO lipid emulsions have plant sterols known as phytosterols, these are thought to alter hepatic function and have been associated with cholestasis in children on long-term PN (29,30). Also, most SO lipid emulsions have small amounts of  $\alpha$ -tocopherol, a known antioxidant. Studies have shown that vitamin E has a role in the prevention of hepatic injury in animal models(31), but there is still deficit in human data.

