Measurements: :**Part A** 1) Patient demography: age, sex; 2) Type of patient: medical, surgical and/or ICU patients; 3) Type of any surgery the patient has during hospitalization; 4) Primary indications related to parenteral nutrition, comorbidities, updated CCI (31,32); 5) Nutritional assessment: weight, height, BMI, SGA, estimated energy and protein requirements; 6) comparison of energy received as a goal vs calculated energy requirements using published equations; 7) Energy, dextrose, aminoacids and lipids received by PN.

Total energy and proteins received including enteral nutrition and oral intake. Energy provided by Propofol, if received. In case of enteral nutrition, name and amount of product used; 8) Type of line used (peripheral or central); 9) Vascular access; 10) Reason for ending PN; 11) Number of times and reasons for interruption of PN; 12) Weekly PN related laboratory results; 13) Complications secondary to PN; 14) Outcome of patient

**Part B:** We will include the same measurements as in part A, but will add some additional nutritional parameters which will be done at baseline (Day 0) and after 10 days (Day 10)

with PN. Baseline or day 0 assessments to be done prior to or within 24 hours of PN initiation. Day 10 measurements to be done on day 10 of PN administration. If the PN ends before day 10, we will consider a cutoff at day 7 of PN. This means that if the PN ends before day 7, we will not repeat the measurements or blood work. If PN ends between days 7-9 we will repeat the measurements instead of doing them on day 10 for this special cases.

The parameters to measure will be: hand grip strength (kg), mid arm circumference (cm), SGA and weight as measures of nutritional status. We will also add hs-CRP, pre-albumin, and fatty acid profile in red blood cells (RBC) and plasma to the laboratory results at both time points. Clinical outcomes (documented infections, antibiotic-days or other adverse events) will be monitored for one week post-PN. In addition, mortality and length of stay will be documented for the entire hospitalization.

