### **Blood sample collection and processing:**

Blood will be collected in the morning during the routine blood draw on the wards. Samples for plasma and RBC fatty acids will be collected in EDTA containing tubes, and

samples for pre-albumin and hs-CRP in tubes without anticoagulant. The tubes will be centrifuged ( $910 \times g$ , 10 min), and serum and plasma will be aliquoted and stored at  $-80^{\circ}C$  until analysis.

From the plasma tube, all remaining plasma and the buffy coat, which shows on top of the erythrocyte sediment as a white ring will be discarded. The remaining packed RBC will be aliquoted and frozen at  $-80^{\circ}C$  until analysis.

Pre-albumin and hs-CRP will be measured by routine methods at an accredited laboratory (Hospitals In-Common Laboratory Inc., Toronto).

Red blood cell and plasma fatty acid profile will be assessed using gas chromatography. Briefly, total lipids will be extracted from RBC or plasma into chloroform/methanol (47), containing butylated hydroxytoluene as antioxidant. Extracted lipids will be saponified and transmethylated using boron-triflouride (48). Fatty acid methyl esters were then separated using an Agilent 6890 gas chromatograph equipped with a flame ionization detector (49). Peaks will be identified from C14:0 to C22:6n-3. The relative amount of the essential fatty acids, alpha-linoleic acid and linolenic acid will be reported as % of total lipids.

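### Part B baseline bloods may be drawn up to 24 hours after the assigned lipid starts, so change from baseline in fast-responding markers can already contain some treatment effect

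*Combined protocol and SAP*

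**What the plan says.** The Measurements text for Part B, under Study design, sets the window: "Baseline or day 0 assessments to be done prior to or within 24 hours of PN initiation". Sampling before PN is listed as its own option, so the 24 hours must include time after PN has started.

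Feasibility and Sample Size, Part B, allocates the emulsion "on an alternate basis (one-to-one) for the duration of the PN". Study lipid therefore starts with PN.

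The blood sampling section fixes the time of day but not the order relative to the infusion: "Blood will be collected in the morning during the routine blood draw on the wards". On recruitment, Study design states for Part A: "Patients will be approached when they start with PN during their hospitalization". It gives no different timing for Part B.

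The second measurement is specified as "Day 10 measurements to be done on day 10 of PN administration", with an exception for shorter courses: "If PN ends between days 7-9 we will repeat the measurements instead of doing them on day 10 for this special cases".

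The Statistical analysis section, Part B, names hs-CRP and pre-albumin among the outcomes that may change over time, together with other laboratory results, and says that "changes will be compared between groups using unpaired t-test or Mann-Whitney test as appropriate". Fatty acids are not named there. The Measurements text adds them to the laboratory results at both time points, so they are covered by inference.

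The plan does not require a sample before the first lipid, a record of the interval from lipid start to draw, adjustment for that interval, or a sensitivity analysis.

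**The concern.** A baseline should describe the patient before the assigned treatment. If some baseline samples are drawn after the lipid has been running, any early difference between the emulsions enters the baseline and is then subtracted from the later difference.

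Plasma fatty acids are the most plausible case, because the infused product is a direct source of what is measured. Background describes Intralipid as rich in omega-6 polyunsaturated fatty acids and ClinOleic as 65% monounsaturated and 20% polyunsaturated. The sampling section reports essential fatty acids as a percentage of total lipids, so a plasma sample taken during infusion could already differ by arm.

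Inflammation, pre-albumin and essential fatty acid status are listed secondary outcomes for Part B, and its stated objective is to compare metabolic, nutritional, infectious and inflammatory parameters. If draw and start times are not captured, a null result on these markers could not be told apart from a contaminated baseline.

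**Working it through.** **The plan's own figure.** There is none for these markers. The only computed figure is 150 per arm for length of stay, which uses no baseline value. For completeness, a difference of 2 days with pooled SD √((5² + 8²)/2) = 6.67, two-sided alpha 0.05 and power 0.8 gives 175 per arm. That is a separate matter and is not evidence here.

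**Expected difference in change.** Let D be the true between-arm difference at day 10 (or days 7-9), q the share of baselines drawn after lipid start (assumed equal in both arms), and e the average between-arm difference already present in those late samples. Then

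expected difference in change = D − q·e.

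- If e has the same sign as D and is smaller, write e = f·D. The difference becomes D(1 − q·f), which is shrinkage.
- If e has the opposite sign, the difference is inflated.
- If lipid shifts both arms equally, e = 0: there is added noise but no bias.

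**Plausible values of f (all assumed; the documents give no response speed).**

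- Linear build-up: a draw at the full 24 hours holds 1/10 = 10% of a day-10 effect, or 1/7 = 14% of a day-7 effect. If late draws spread evenly over 0-24 hours, average exposure is 12 hours and f is about 5% of a day-10 effect.
- Approach to a plateau with half-life h days: f = (1 − 2^(−1/h)) / (1 − 2^(−10/h)) for a draw at 24 hours. For h = 10, 5, 2 and 1 this gives 13%, 17%, 30% and 50%.

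**Power.** Take a comparison that would have 80% power with a clean baseline, and assume the SD of the change is unaffected. Then

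power = Φ(2.80 × (1 − q·f) − 1.96).

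Each cell shows the share of the difference lost and the resulting power:

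| q | f = 5% | f = 10% | f = 20% | f = 40% |
|---|---|---|---|---|
| 25% | 1.25%, 79% | 2.5%, 78% | 5%, 76% | 10%, 71% |
| 50% | 2.5%, 78% | 5%, 76% | 10%, 71% | 20%, 61% |
| 100% | 5%, 76% | 10%, 71% | 20%, 61% | 40%, 39% |

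With q = 0 nothing is lost and power stays at 80%.

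**Would discarding post-start samples help?** If a share m of baselines is treated as missing, power becomes Φ(2.80 × √(1 − m) − 1.96). At m = 50%, 75 of 150 per arm remain and power is about 51%, below every value in the q = 50% row. Discarding costs more power than a 10% attenuation once m exceeds 1 − 0.9² = 19%, and more than a 20% attenuation once m exceeds 1 − 0.8² = 36%.

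**The case against.** A 24-hour window is a pragmatic choice in an inpatient study where PN starts according to need, and nothing in the plan contradicts it. Three parts of the case against stand.

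First, a reader might infer from Background that a day of Intralipid is already known to move these markers, since a 24-hour infusion study is cited there. It does not show that. The study had 12 healthy subjects, and the result the protocol reports is that "the authors found that Intralipid increased blood pressure and altered endothelial function". Neither is a Part B outcome, and no 24-hour result for hs-CRP, pre-albumin or fatty acids is given. The citation shows only that a day of lipid should not be presumed inert.

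Second, a reader might infer a sizeable loss of power. That requires both many late draws and a fast response. Under linear build-up with half the draws late and spread over the window, power falls only from 80% to about 78%. RBC fatty acids may hardly move in a day. The objectives also plan to record how many days patients take to reach their requirements, so full feeding on day 1 is not assumed.

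Third, a reader might infer that the bias must run towards no difference. It does so only if early and later effects share a direction.

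What the objection does not remove is the mechanism. The window permits sampling on study lipid, a patient who starts PN after the morning draw would have the next routine sample after exposure, and the change analysis makes no allowance for it.

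**Conclusion.** The point holds as a possible, unquantified distortion of secondary change endpoints: hs-CRP, pre-albumin and, by inference, fatty acids, with plasma fatty acids the most plausible case. Length of stay, mortality, infections, ICU days and antibiotic-days use no baseline value and are untouched.

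The documents give neither the share of baselines drawn after the start nor the share of the effect then present. With 50% and 5-40% assumed, 2.5-20% of the between-arm difference is lost, and a hypothetical 80% power falls to about 78-61%. These figures also assume effects in the same direction, equal shares of late draws in both arms, and an unchanged SD. The plan states no power for these markers, so 80% is a reference level only. This is a cheap improvement to make, not a flaw that threatens the trial's main comparison.

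**What to change.** In the Part B Measurements text, require the baseline sample for plasma and RBC fatty acids, hs-CRP and pre-albumin to be drawn before the first lipid infusion where feasible, using the routine morning draw. Keep the 24-hour allowance for SGA, weight, arm circumference and grip strength.

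Record the time of the draw and the time the lipid starts. In the Statistical analysis section, keep post-start samples in the main analysis and pre-specify a sensitivity analysis restricted to patients with pre-lipid baselines. Do not treat post-start samples as missing: if they are common this loses more power than it saves, and the losses may not be random, for example if they fall on patients who start PN quickly. Using a contaminated value as a regression covariate would not fully remove the problem either.

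The tubes and assays are unchanged, and only sampling is affected. The cost is two recorded times, one extra analysis, and tighter coordination of consent and the morning draw with the start of PN.
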